10.3.1. Safety Analyses

10.3.1.1. Clinical Evaluation of Safety

All IMP and protocol procedure-related AEs will be listed, and if the frequency of events allows, safety data will be summarized using descriptive methodology.

The incidence of symptoms for each treatment group will be presented by severity and by association with IMP as perceived by the investigator. Symptoms reported to occur before the first IMP dosing will be distinguished from those reported as new or increased in severity during the study. Each symptom will be classified by the most suitable term from the Medical Dictionary for Regulatory Activities.

The number of IMP-related SAEs will be reported.

10.3.1.2. Statistical Evaluation of Safety

Safety parameters that will be assessed include safety laboratory parameters, vital signs, ECG parameters, injection-site reactions, and hypoglycemia. The parameters will be listed and summarized using standard descriptive statistics.

Laboratory measurements will be summarized with respect to observed values and change from baseline by treatment group at each time point using descriptive statistics. In addition, all clinical chemistry, hematology, and urinalysis data outside the reference ranges will be tabulated by parameter and treatment group.

Vital signs will be summarized with respect to observed values and change from baseline (Day 1, Predose) by treatment at each time point using descriptive statistics. For change from baseline values, a mixed-model repeated-measure model with treatment, time (of measurement), and treatment-by-time interaction as fixed effects, patient as random effect, and baseline as covariate will be used to determine the effects of LY3298176.

Electrocardiogram parameters, including the pulse rate, QT interval, RR interval, and QTc using Fridericia's formula (QTcF), QRS interval duration, and heart rate, will be summarized. The number and percentage of patients with a maximum increase from baseline in QTcF will be summarized for each treatment group according to the following categories: >30 milliseconds and >60 milliseconds. In addition, the number and percentage of patients with QTcF postdose values according to the following categories: >450 milliseconds, >480 milliseconds, and >500 milliseconds, will be summarized by treatment group. Exploratory analyses may be performed to determine the effects of LY3298176 concentration-response analysis of QTcF.

Additional analysis will be performed, if warranted, upon review of the data.

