Informed consent	X						
Distribution of glucose meters, test strips, and diaries/SMPG training	X ^e	X					
7-point SMPG		X ^f					
Medical history	X						
Physical examination	X						
Medical assessment	X			X	X	X	
AEs/concomitant medications	X			X	X	X	X
Chest x-ray ^g	X						
Height and weight	X						
Body temperature	X						
Vital signs (BP/PR) ^{h,i}	X			X	X	X	
12-Lead ECG ^{i,j}	X			X	X	X	
PK sampling ^{k,l}				X	X	X	X
Clinical safety lab (hematology, chemistry, urinalysis) ^{m,n}	X			X	X	X	
Clinical safety lab (serology) ⁿ	X						
Pregnancy test (serum, urine) ^{n,o,p}	X						
Follicle-stimulating hormone ^{n,o}	X						
Urine drug and alcohol screen ^{n,p}	X						
Hemoglobin A1c ^{l,m}	X						
Fasting glucose, insulin, glucagon ^{l,m}				X	X	X	
Immunogenicity ^l					X	X	X

Study Schedule Protocol I8F-JE-GPGC Cohort 1 for Treatment Period

Procedure	Treatment Period (Cohort 1)																					
	-1	1	2	3	4	8	15	16	17	18	22 ±1	29	30	31	32	36 ±1	43 ±1	50	51	52	57	ET1 ^d
Inpatient stay at CRU ^q	X	X	X	X	X		X	X	X	X		X	X	X	X		X	X	X			
Outpatient visits to CRU						X					X					X	X				X	X
Remind Patients about 7-point SMPG						X					X					X				X		
7-point SMPG							X					X					X				X	
Randomization		X																				
IMP administration ^r		X				X	X up-titra- tion				X	X up-titra- tion				X	X	X				
Medical assessments		Pre	X	X	X	X	X	X	X	X	X	X	X	X	X	X	X	X	X	X	X	
AEs/concomitant medications	X	X	X	X	X	X	X	X	X	X	X	X	X	X	X	X	X	X	X	X	X	
Weight ^t		Pre				Pre	Pre				Pre	Pre				Pre	Pre	Pre			X	X
Body temperature	X	Pre																				X
Vital signs (BP/PR) ^{h,i}	X	Pre, 1, 4, 8, 12	24	48	72	Pre	Pre	24	48	72	Pre	Pre	24	48	72	Pre	Pre	Pre			168	X
12-Lead ECG ^{i,j}		Pre, 8	24	48	72	Pre	Pre				Pre	Pre				Pre	Pre	Pre,	8	24	168	X
PK sampling ^{k,l}		Pre, 8	24	48	72	Pre	Pre				Pre	Pre				Pre	Pre	Pre,	8	24	48	168
Clinical safety lab (hematology, chemistry, urinalysis) ^{m,n}	X		24	48		Pre	Pre	24	48		Pre	Pre	24	48		Pre	Pre	Pre	24	48	168	X
OGTT ^{l,u}	X																			X		
Hemoglobin A1c ^{l,m}		Pre										Pre									168	X
Fasting glucose, insulin, glucagon ^{l,m}		Pre	24			Pre	Pre	24			Pre	Pre	24			Pre	Pre	Pre	24 ^v		168	X
Meal intake and appetite ^w	L/D		L/D																L/D			
Lipid panel ^{l,m,x}		Pre									Pre								24			X

Study Schedule Protocol I8F-JE-GPGC Cohort 1 for Treatment Period

Procedure	Treatment Period (Cohort 1)																				
	-1	1	2	3	4	8	15	16	17	18	22 ±1	29	30	31	32	36 ±1	43 ±1	50	51	52	57

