Exploratory storage samples ^{l,m,y}		Pre				Pre												24			X
Pharmacogenetic sample ^l		Pre																			
Nonpharmacogenetic sample (storage) ^{l,m}		Pre					Pre					Pre				Pre	Pre			168	X
Immunogenicity ^l		Pre									Pre									168	X

Study Schedule Protocol I8F-JE-GPGC Cohort 2 for Treatment Period

Procedure	Treatment Period (Cohort 2)																					
	-1	1	2	3	4	8	15	16	17	18	22 ±1	29 ±1	36 ±1	43	44	45	46	50	51	52	57	ET1 ^d
Inpatient stay at CRU ^q	X	X	X	X	X		X	X	X	X				X	X	X	X	X	X	X		
Outpatient visits to CRU						X	X				X	X	X	X							X	X
Remind Patients about 7-point SMPG						X					X		X								X	
7-point SMPG							X					X		X								X
Randomization		X																				
IMP administration ^r		X				X	X up-titra- tion				X	X	X	X up-titra- tion				X				
Medical assessments		Pre	X	X	X	Pre	Pre	X	X	X	Pre	Pre	Pre	Pre	X	X	X	Pre	X	X	X	
AEs/concomitant medications	X	X	X	X	X	X	X	X	X	X	X	X	X	X	X	X	X	X	X	X	X	
Weight ^t		Pre				Pre	Pre				Pre	Pre	Pre	Pre				Pre			X	X
Body temperature	X	Pre																				X
Vital signs (BP/PR) ^{h,i}	X	Pre, 1, 4, 8, 12	24	48	72	Pre	Pre	24	48	72	Pre	Pre	Pre	Pre	24	48	72	Pre			168	X
12-Lead ECG ^{i,j}		Pre, 8	24	48	72	Pre	Pre				Pre	Pre	Pre	Pre				Pre, 8	24		168	X
PK sampling ^{k,l}		Pre, 8	24	48	72	Pre	Pre				Pre	Pre	Pre	Pre				Pre, 8	24	48	168	X
Clinical safety lab (hematology, chemistry, urinalysis) ^{m,n}	X		24	48		Pre	Pre	24	48		Pre	Pre	Pre	Pre	24	48		Pre	24	48	168	X
OGTT ^{l,u}	X																				X	
Hemoglobin A1c ^{l,m}		Pre									Pre										168	X
Fasting glucose, insulin, glucagon ^{l,m}		Pre	24			Pre	Pre	24			Pre	Pre	Pre	Pre	24			Pre	24 ^v		168	X
Meal intake and appetite ^w	L/D		L/D															L/D				
Lipid panel ^{l,m,x}		Pre									Pre							24				X

Study Schedule Protocol I8F-JE-GPGC Cohort 2 for Treatment Period

Procedure	Treatment Period (Cohort 2)																					
	Days	-1	1	2	3	4	8	15	16	17	18	22 ±1	29 ±1	36 ±1	43	44	45	46	50	51	52	57
Exploratory storage samples ^{l,m,y}		Pre				Pre													24			X
Pharmacogenetics sample ^l		Pre																				
Nonpharmacogenetic sample (storage) ^{l,m}		Pre					Pre					Pre		Pre				Pre			168	X
Immunogenicity ^l		Pre									Pre										168	X

Study Schedule Protocol I8F-JE-GPGC Cohort 3 for Treatment Period

Procedure	Treatment Period (Cohort 3)															ET1 ^d
	-1	1	2	3	4	8	15 ±1	22 ±1	29 ±1	36 ±1	43 ±1	50	51	52	57	
Days																
Inpatient stay at CRU ^q	X	X	X	X	X							X	X	X		

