Outpatient visits to CRU						X	X	X	X	X	X				X	X
Remind Patients about 7-point SMPG						X		X		X				X		
7-point SMPG							X		X		X				X	
Randomization		X														
IMP administration ^r		X				X	X	X	X	X	X					
Medical assessments ^s		Pre	X	X	X	Pre	Pre	Pre	Pre	Pre	Pre	Pre	Pre	X	X	X
AEs/concomitant medications	X	X	X	X	X	X	X	X	X	X	X	X	X	X	X	X
Weight ^t		Pre				Pre	Pre	Pre	Pre	Pre	Pre	Pre			X	X
Body temperature	X	Pre														X
Vital signs (BP/PR) ^{h,i}	X	Pre, 1, 4, 8, 12	24	48	72	Pre	Pre	Pre	Pre	Pre	Pre				168	X
12-Lead ECG ^{i,j}		Pre, 8	24	48	72	Pre	Pre	Pre	Pre	Pre	Pre	Pre,	24		168	X
PK sampling ^{k,l}		Pre, 8	24	48	72	Pre	Pre	Pre	Pre	Pre	Pre	Pre,	24	48	168	X
Clinical safety lab (hematology, chemistry, urinalysis) ^{m,n}	X		24	48		Pre	Pre	Pre	Pre	Pre	Pre	24	48	168		X
OGTT ^{l,u}	X													X		
Hemoglobin A1c ^{l,m}		Pre							Pre						168	X
Fasting glucose, insulin, glucagon ^{l,m}		Pre	24			Pre	Pre	Pre	Pre	Pre	Pre	24 ^v		168		X
Meal intake and appetite ^w	L/D		L/D											L/D		
Lipid panel ^{l,m,x}		Pre							Pre					24		X
Exploratory storage samples ^{l,m,y}		Pre				Pre								24		X
Pharmacogenetics sample ^l		Pre														
Nonpharmacogenetic sample (storage) ^{l,m}		Pre					Pre		Pre		Pre				168	X
Immunogenicity ^l		Pre						Pre							168	X

Study Schedule Protocol I8F-JE-GPGC

Abbreviations: ADA = antidrug antibody; AE = adverse event; BP = blood pressure; CRU = clinical research unit; D = dinner; DPP = dipeptidyl peptidase; ECG = electrocardiogram; ET = early termination; IMP = investigational medicinal product; L = lunch; lab = laboratory tests; OGTT = oral glucose tolerance test; PK = pharmacokinetic; PR = pulse rate; SMPG = self-monitored plasma glucose.

Note: numbers are in hours in relation to dosing; Pre = predose.

- a Screening shall be completed up to 28 days before treatment assignment. Patients treated with metformin or DPP-IV inhibitors (except for omarigliptin, trelagliptin, and linagliptin) will be required to withdraw their treatment and have at least a-28-day washout period before dosing with IMP.
- b Patients who passed screening tests will visit the CRU to receive glucose meters, test strips, and diaries for 7-point SMPG before Day -1.
- c Only for the patients who have clinically significant treatment-emergent antidrug antibodies. Refer to Section 9.6.4 for details.

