Appendix 7. Blood Sampling Summary

This table summarizes the approximate number of samples and blood volumes for all blood sampling (screening, safety laboratories, bioanalytical assays, and the other tests) during the study.

Protocol I8F-JE-GPGC Sampling Summary

Purpose	Blood Volume per Sample (mL)	Number of Blood Samples		Total Volume (mL)	
		Cohort 1 or 2	Cohort 3	Cohort 1 or 2	Cohort 3
Screening serology and Serum pregnancy tests ^a	9 ^b	1	1	9	9
Clinical safety laboratory tests ^a	10 ^b	20	16	200	160
Lipid panel	2.5	3	3	7.5	7.5
LY3298176 pharmacokinetics	3	18	18	54	54
Potential additional LY3298176 pharmacokinetic samples	3	3	3	9	9
Glucagon	2	15	13	30	26
Fasting plasma glucose and insulin	4.5	15	13	67.5	58.5
Oral glucose tolerance test (serum glucose and insulin)	2.5	10	10	25	25
HbA1c	2	4	4	8	8
Immunogenicity	6	4	4	24	24
Exploratory storage sample ^d					
Adiponectin	2	2	2	4	4
Cortisol	2.5	3	3	7.5	7.5
Bone biomarkers	3.5	2	2	7	7
Pharmacogenetics	6	1	1	6	6
Nonpharmacogenetics Storage sample	4.5	6	6	27	27
Total				485.5 ^c	432.5 ^c

Abbreviation: HbA1c = hemoglobin A1c.

^a Additional samples may be drawn if needed for safety purposes.

^b Because screening and safety (chemistry and hematology) tests are performed at local laboratories at each site, this volume is an estimate and will vary depending on the local laboratory's testing requirements.

^c The maximum blood volume will increase if follow-up visits for antidrug antibody testing are needed.

^d Blood volumes for this storage sample is calculated based on the assumption that the following biomarkers will be assayed for.

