9.5 Safety and Tolerability Assessments

9.5.1 Adverse events

Where changes in severity are recorded in the Case Report Form (CRF), each separate severity of the AE will be reported in the listings, only the most severe will be used in the summary tables. A pre-existing condition is defined as an AE that starts before the patient has provided written informed consent and is ongoing at consent. A non-treatment emergent AE is defined as an AE which starts after informed consent but prior to dosing. A treatment-emergent AE (TEAE) is defined as an AE which occurs postdose or which is present prior to dosing and becomes more severe postdose. AEs will also be presented by day of onset.

All AEs will be listed. TEAEs will be summarized by treatment regimen, severity, and relationship to the study drug. The frequency (the number of AEs, the number of patients experiencing an AE and the percentage of patients experiencing an AE) of TEAEs will be summarized by treatment regimen, Medical Dictionary for Regulatory Activities (MedDRA) version 20.0 system organ class, and preferred term. The summary and frequency AE tables will be presented for all causalities and those considered related to the study drug. Any serious AEs will be tabulated.

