9.5.10 Glucose Monitoring and Hyperglycemia/Hypoglycemia Reporting

Hypoglycemic events will be appropriately recorded in the CRF. In the case of a hypoglycemic event, the actual blood glucose value, if measured, will be recorded in the CRF, together with any treatments administered. Each category of hypoglycemic event (defined below) will be listed and summarized by treatment regimen.

Blood glucose levels will be listed for individual patients and summarized by treatment regimen.

Hyperglycemia and Hypoglycemia

Hyperglycemic events will be reported by the investigator or designated physician who will be responsible for advising the patient on what further actions to take. Hypoglycemic events will be recorded in the CRF, together with any treatments administered.

The main categories of hypoglycemia are as follows:

- **Documented Glucose Alert Level (Level 1):** plasma/serum glucose ≤ 70 mg/dL (3.9 mmol/L)
 - **Documented symptomatic hypoglycemia:** with typical symptoms of hypoglycemia.
 - **Documented asymptomatic hypoglycemia:** without typical symptoms of hypoglycemia.

- **Documented unspecified hypoglycemia:** with no information about symptoms of hypoglycemia available. (This has also been called unclassifiable hypoglycemia.)
- **Documented Clinically Significant Hypoglycemia (Level 2):** with similar criterion as above except for threshold plasma/serum glucose <54 mg/dL (3.0 mmol/L)
 - **Symptomatic hypoglycemia:** an event during which typical symptoms of hypoglycemia are accompanied by PG <54 mg/dL (3.0 mmol/L)
 - **Asymptomatic hypoglycemia:** an event not accompanied by typical symptoms of hypoglycemia but with PG <54 mg/dL (3.0 mmol/L)
 - **Unspecified hypoglycaemia:** an event during which PG <54 mg/dL (3.0 mmol/L) but no information relative to symptoms of hypoglycemia was recorded
- **Severe Hypoglycemia (Level 3)**

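### Cohorts 1 and 2 have 18 scheduled postdose safety-laboratory draws against 14 in Cohort 3, so any-time laboratory-driven counts by regimen can run modestly higher under titration from sampling frequency alone

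*Protocol*

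**What the plan says.** **Protocol 10.3.1.2** says that "all clinical chemistry, hematology, and urinalysis data outside the reference ranges will be tabulated by parameter and treatment group". It does not say whether patients or values are counted, and sets no common time points.

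**SAP 9.5.3** provides only for listing the out-of-range values. SAP 3 states that the SAP takes precedence over the protocol's statistical section and that substantial differences will be identified. SAP 11 reports no changes.

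**SAP 9.5.10**, on hypoglycemia: "Each category of hypoglycemic event (defined below) will be listed and summarized by treatment regimen". Under Protocol 9.4.4.4.1, a plasma or serum glucose of 70 mg/dL or less is a Level 1 event even without symptoms. Protocol Appendix 2 includes glucose in the local fasting chemistry panel.

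**SAP 9.5.1**: "TEAEs will be summarized by treatment regimen, severity, and relationship to the study drug", with numbers and percentages of patients.

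**SAP 8** pools placebo patients across cohorts for safety.

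**Protocol Appendix 7** gives safety-laboratory samples per patient, for Cohorts 1 or 2 and then Cohort 3: "Clinical safety laboratory tests ^a 10 ^b 20 16 200 160". That is 20 against 16 samples.

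**The concern.** Each active regimen is given in one cohort only, so a difference in visit schedule between cohorts is also a difference between regimens. Cohorts 1 and 2 return to inpatient observation after each of two up-titrations. Between Day 8 and Day 50, Cohort 3 has weekly visits only. The chance that a patient ever shows an abnormal value grows with the number of samples taken, so a table of any-time findings by regimen mixes drug effect with sampling frequency. Pooled placebo matches neither schedule.

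The timing adds to this. Protocol 3.2 puts peak concentration at 1 to 2 days postdose, which is where the extra draws fall. A transient finding is more likely to be caught in the titrated regimens.

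Safety is the primary objective, and Protocol 5.4 says the data will support the choice of dose range for later studies in Japan.

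**Working it through.** **1. Reproduce the plan's count.** Draws are read from the schedules in Protocol Section 2, leaving out early-termination visits.

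- Cohort 1, "Clinical safety lab (hematology, chemistry, urinalysis) ^{m,n} X 24 48 Pre Pre 24 48 Pre Pre 24 48" and onward: Days 2, 3, 8, 15, 16, 17, 22, 29, 30, 31, 36, 43, 50, 51, 52, 57 = 16. Adding Days 64 and 85 gives 18 postdose. With screening and Day -1 the total is 20, as in Appendix 7.
- Cohort 2, "Clinical safety lab (hematology, chemistry, urinalysis) ^{m,n} X 24 48 Pre Pre 24 48 Pre Pre Pre Pre 24 48" and onward: the same, with Days 44 and 45 in place of 30 and 31. Again 18 postdose and 20 in total.
- Cohort 3, "Clinical safety lab (hematology, chemistry, urinalysis) ^{m,n} X 24 48 Pre Pre Pre Pre Pre Pre 24 48 168": the row as extracted from the PDF shows 11 draws, plus Days 64 and 85 = 13, or 15 in total. Appendix 7's 16 implies a Day 50 predose draw that the extracted row does not show. With it there are 14 postdose draws.

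The excess is 18 − 14 = 4 draws: Days 16 and 17, plus 30 and 31 (Cohort 1) or 44 and 45 (Cohort 2). Draws at 24 to 48 h number 8 in Cohorts 1 and 2 against 4 in Cohort 3.

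**2. Pooled placebo.** There are 3 + 3 + 3 = 9 patients, six on the denser schedule. Mean draws = (6 × 18 + 3 × 14)/9 = 16.7.

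**3. Null gap, patients with at least one finding, per analyte.** The per-draw rate p is assumed. With independent draws the share is 1 − (1 − p)^k. The placebo column is (6 × share at 18 + 3 × share at 14)/9. Gaps are from unrounded values.

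| p | k = 18 | k = 14 | Pooled placebo | Gap, 18 vs 14 |
|---|---|---|---|---|
| 0.5% | 8.6% | 6.8% | 8.0% | 1.9 |
| 1% | 16.5% | 13.1% | 15.4% | 3.4 |
| 2.5% | 36.6% | 29.8% | 34.3% | 6.8 |
| 5% | 60.3% | 51.2% | 57.3% | 9.0 |

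In patients out of 12: 12 × 0.034 = 0.4 at 1%, and 12 × 0.090 = 1.1 at 5%.

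**4. The same with within-patient correlation.** Under a beta-binomial with correlation ρ, the share is 1 − B(a, b + k)/B(a, b), where a = p(1 − ρ)/ρ and b = (1 − p)(1 − ρ)/ρ. The values of ρ are also assumed.

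| p | ρ | k = 18 | k = 14 | Gap |
|---|---|---|---|---|
| 1% | 0.3 | 5.4% | 4.9% | 0.5 |
| 1% | 0.6 | 2.8% | 2.6% | 0.2 |
| 5% | 0.3 | 24.4% | 22.4% | 2.0 |
| 5% | 0.6 | 13.3% | 12.5% | 0.7 |

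**5. If values are counted instead of patients**, the expected count is k × p. With full follow-up the null ratio is 18/14 = 1.29 whatever the correlation.

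**6. Dropout.** Protocol 10.1 expects 30% in Cohorts 1 and 3 and 50% in Cohort 2. Assume dropout spread evenly over time, with both early-termination visits attended. Expected draws are then (1 − d)k + d[(k − 2)/2 + 2]:

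- Cohort 1: 0.7 × 18 + 0.3 × 10 = 15.6
- Cohort 2: 0.5 × 18 + 0.5 × 10 = 14.0
- Cohort 3: 0.7 × 14 + 0.3 × 8 = 12.2

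The excess over Cohort 3 falls from 4 to 3.4 draws in Cohort 1 and to 1.8 in Cohort 2.

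**7. Common days.** All 14 Cohort 3 draw days (2, 3, 8, 15, 22, 29, 36, 43, 50, 51, 52, 57, 64, 85) are scheduled in every cohort. Restricting to them gives 14/14/14 and discards nothing postdose from Cohort 3.

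**The case against.** The strongest reply is that little of the operative plan depends on the number of draws. The SAP lists out-of-range values, and Protocol 10.3.1.2 never defines a count of patients with at least one, so steps 3 and 4 size a table that may not be produced. This stands in part. The SAP text would govern, but SAP 11 declares no change from the protocol, so the tabulation has not clearly been withdrawn.

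On hypoglycemia, patients monitor glucose throughout, and seven-point profiles fall on the same study days in every cohort, so four extra chemistry panels add little. This reduces the gap but does not remove it: an asymptomatic low laboratory glucose still counts as Level 1. Non-severe hypoglycemia is not recorded as an adverse event, so it does not also inflate the TEAE tables.

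Independence is implausible for repeated values in one patient. That is right, and the correlated figures are the more realistic ones for patient counts.

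Protocol 7.1 frames the study against placebo, and Protocol 5.5 includes Cohort 3 for comparison with Study GPGA. Against pooled placebo, the titrated excess under independence is only 1.1 points at 1% per draw and 3.0 at 5%. These counts are descriptive, with no planned test.

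A reader might go further and infer that every harm count is inflated, because vital-sign readings also differ (23 against 17, the latter assuming a Day 50 predose reading not visible in the extracted row), as do adverse-event review days (22 against 16). The documents do not support that. Vital signs are summarized and modelled by time, with no any-time count. Adverse events are recorded continuously after consent, so review days are opportunities to ask, not the recording window. The QTcF maximum-increase categories rest on 16 postdose ECG times in every cohort.

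**Conclusion.** The difference in sampling is certain; its effect is modest and confined to laboratory-driven any-time counts. These are documented hypoglycemia detected from scheduled laboratory glucose, and out-of-range values if they are tabulated. For patient counts, the null gap between a titrated regimen and fixed 5 mg is about 0.2 to 2 points per analyte, assuming 1% to 5% per draw and within-patient correlation of 0.3 to 0.6. It is up to 9 points if draws are independent at 5%. None of these rates is in the documents. If values are counted, the ratio is 1.29 before dropout.

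It would be wrong to conclude that the titrated regimens will look less safe. The documents show only that these counts can be somewhat higher for a reason unrelated to the drug. The regimens also differ in dose, and a real dose effect cannot be separated from sampling frequency in an all-visit count alone. This is an inexpensive improvement, not a flaw in the primary safety assessment.

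**What to change.** 1. Reconcile Protocol 10.3.1.2 (tabulated), SAP 9.5.3 (listed) and SAP 11 (no changes). If a table is intended, state whether it counts patients or values.
2. In SAP 9.5.3 and 9.5.10, for any between-regimen count of out-of-range values or of hypoglycemia detected from a scheduled laboratory sample, show the count on the 14 common draw days beside the all-visit count. Apply the same filter to pooled placebo.
3. Footnote the TEAE tables to say that Cohorts 1 and 2 had six more adverse-event review days than Cohort 3 (22 − 16).

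The cost is SAP wording and one visit filter in programming, with no new data. The common-day count leaves out the post-titration draws, where a real transient effect might appear, so it must supplement the all-visit count and not replace it.

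Two further steps are not recommended. Setting Cohort 3 against its own three placebo patients makes one patient worth 33 points (1/3), far more than the bias it would correct. Splitting TEAEs by how they were detected needs a data field that the documents do not describe.
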